8.6.5 Treatment Compliance

As is customary for contact lens solution trials, treatment compliance will not be evaluated.

8.6.6 Treatment Exposure

As is customary for contact lens solution trials, treatment exposure will not be evaluated.

8.6.7 Missing Data

Imputation of missing data is not conservative in a non-inferiority analysis setting. Therefore, primary effectiveness analyses will be completed using the PP Set without imputation of missing data.

Sensitivity analyses of data from the ITT Set with missing data imputation are described in Section 8.6.1 above. Unless otherwise specified in the protocol or statistical analysis plan, missing data will not be imputed.

8.6.8 Interim Analyses

No interim analyses are planned.

9.0 DATA QUALITY ASSURANCE

9.1 Study Monitoring

Bausch + Lomb Clinical Operations representatives must be allowed to visit all study site locations to assess the data, quality, and study integrity in a manner consistent with applicable health authority regulations and the procedures adopted by Bausch + Lomb Clinical Operations.

Prior to the start of the study, member(s) of the Bausch + Lomb Clinical Operations, Clinical Affairs, and Global Regulatory Affairs will review the protocol, eCRF, regulatory obligations, and other material or equipment relevant to the conduct of the study with the Investigator/Sub-Investigator and relevant study site personnel.

Monitoring visits and telephone consultations will occur as necessary, or per the monitoring plan, during the course of the investigation to verify the following:

- the rights and well-being of subjects are protected
- the conduct of the investigation is in compliance with the currently approved protocol/amendment, 21CFR Parts 50, 54, 56 and 812, 42 USC 282(j) and with consideration of the provision in: ISO 14155-1:2009 Clinical investigation of medical devices for human subjects – Part 1: General requirements; 14155-2:2009 Part 2:

Clinical investigation of medical devices for human subjects – Part 2: Clinical investigational plan; ISO 11980:2009 Ophthalmic Optics – Contact Lenses and contact lens care products – Guidance for clinical investigations; ICH GCPs; and applicable local regulations.

- the integrity of the data, including adequate study documentation
- the facilities remain acceptable
- the Investigator and site personnel remain qualified and able to conduct the study
- test article accountability

During the course of the study, if the Sponsor determines that an Investigator is not compliant with the protocol and/or applicable regulatory requirements, the Sponsor will take action to secure compliance. In addition, the Sponsor may terminate the Investigator's participation in the study if appropriate, or if the Investigator remains non-compliant despite the Sponsor's actions.

9.2 Source Documentation

All medical information obtained at each study visit must be recorded in the subject's record (source documentation) in real time as it is collected. Source documentation consists of original subject documents, as well as data and records with information relevant to the subject and his/her participation in the study.

Examples of source documents include: hospital records, clinical and office charts, laboratory notes, memoranda, signed ICFs, evaluation checklists, recorded data from automated instruments, copies or transcriptions certified after verification as being accurate copies, and information initially recorded in an electronic format. Source documentation worksheets may be provided by the Sponsor to record pertinent information.

Subject completed forms are also considered to be source data. In no instance, should an Investigator or study site personnel record any data or make changes to subject completed forms. The Investigator or designee should review subject completed forms during study visits for completeness and accuracy. If an entry is found to be illegible or a mistake is found (e.g., incorrect year was recorded), the subject should be instructed to edit the entry by drawing a single line through the original entry, entering the new information, and dating and initialing the change.

9.3 Electronic Case Report Forms and Data Verification

Subject data required by this protocol are to be transferred from the source to the eCRFs. The Investigator and his/her study site personnel will be responsible for completing the eCRFs. The Investigator is required to verify that all of the requested information is accurately recorded on the eCRFs. All information required on the eCRFs needs to be supplied, including subject identification and initials, date(s), assessment values, etc., and any omission or discrepancy will require explanation. All information on eCRFs must be traceable to source documents.

The CRA will be responsible for reviewing and verifying the data recorded on the eCRFs, utilizing the original source documentation, and will query discrepant findings. The Investigator and study site personnel will be responsible for answering all queries.

The eCRF data will be reviewed for completeness, accuracy, consistency, and medical sense. Programmed edit checks will be used to reduce data entry errors and identify unusual data for verification prior to statistical analysis.

A copy of the eCRF data will be retained at the conclusion of the study by the Investigator, who must ensure that it is stored in a secure place.

9.4 Recording of Data and Retention of Documents

Subject data recorded on eCRFs during the study will be documented to maintain subject confidentiality. The subject will only be identified by the subject number and by initials. Confidentiality of subject's records must be maintained to ensure adherence to applicable local privacy regulations.

The investigators have to retain records for 2 years after the investigational product is approved by the FDA. The Investigator agrees to adhere to the document retention procedures when signing the protocol Investigator Statement of Approval.

Essential documents include but are not limited to the following:

- Device Investigator Agreement
- IRB approvals for the study protocol, all amendments, ICF(s), and advertisements
- IRB annual study review
- IRB correspondence and reports (e.g., AE reports, protocol deviations, and safety updates)
- regulatory documents (e.g., financial disclosure and delegation of authority forms)
- all source documents
- eCRFs
- subject's signed ICF (including HIPAA)
- accountability records for the test article(s)
- correspondence from and to the Sponsor
- any other documents relevant to the conduct of the study

In the event that study records are transferred to another location, the Investigator will provide notice of such transfer in writing to Bausch + Lomb Clinical Operations.

9.5 Auditing Procedures

Audits of clinical research activities in accordance with the Sponsor's internal Standard Operating Procedures to evaluate compliance with the principles of GCP may take place. A regulatory authority may also wish to conduct an inspection (during the study or after its completion). If an inspection is requested by a regulatory authority and/or IRB, the Investigator must inform the Sponsor immediately that this request has been made.

9.6 Institutional Review Board

The Investigator should ensure that the following are approved by their institution IRB, or if not using their institution's IRB, approved by the reviewing central IRB prior to entering any subjects in the study:

- The protocol
- The Investigator's participation in the study
- Subject recruitment materials (written information or materials including web pages, radio advertisements, television spots or written text developed to encourage subject enrollment)
- The ICF to be used in this study.

Documentation of IRB approval of the study protocol and informed consent must be provided to the Sponsor prior to initiation of the study. In addition, the Investigator must

ensure that the reviewing IRB has provided approval for any protocol amendments prior to implementation. If the amendment necessitates a revision to the ICF, the Investigator should ensure the revised form is also submitted to and approved by the Sponsor and the IRB and implemented as directed.

9.7 Publication of Results

All study data generated as a result of this study will be regarded as confidential, until appropriate analysis and review by the Sponsor or its designee and the Investigator(s) are completed. The results of the study may be published or presented by the Investigator(s) after review by, and in consultation and agreement with, the Sponsor, and such that confidential or proprietary information is not disclosed.

Prior to publication or presentation, a copy of the final text should be forwarded by the Investigator(s) to the Sponsor or its designee, for comment. Such comments shall aim to ensure the scientific integrity of the proposed publications and/or presentations and ensure that the data and material referring to Bausch + Lomb products and activities receive fair, accurate, and reasonable presentation.

APPENDIX A: SCHEDULE OF VISITS AND PARAMETERS

All study tasks should be performed by qualified study site personnel as indicated on the delegation of authority log under the supervision of the Principal Investigator.

PROCEDURES / ASSESSMENTS	Screening/Dispensing	2-Week Follow-up Visit	1-Month Follow-up Visit	2-Month Follow-up Visit	3-Month Follow-up Visit	Exit Visit	Unscheduled Visit	Post Study Follow-Up Visit
	Day 0	Day 10-18	Day 26-34	Day 53-67	Day 83-97			
Informed Consent / HIPAA Authorization	X							
Eligibility	X							
Demographics	X							
Adverse events, Culture taken		X	X	X	X		X	
Baseline Lens / Lens Care History	X							
Lens Wear Parameters	X	X	X	X	X		X	
Initial Lens Performance Assessment Form (Worn Lenses Performance Rating Scales)	X							
Lens Performance Assessment Form (Study Lenses Performance Rating Scales)	X	X	X	X	X		X	
Exit Form (if an Exit Visit took place)	X ^a	X	X	X	X	X	X	X
Subject Completed Forms								
Initial Symptoms/Complaints ^b (Worn Lenses Symptoms/Complaints Form)	X							
Symptoms/Complaints (Abbreviated Study Lenses Symptoms/Complaints)	X							
Symptoms/Complaints Form ^b (Study Lenses Symptoms/Complaints)		X	X	X	X		X	
Without Lenses								
Spherocylindrical refraction	X					X		X
High contrast distance BSCVA	X					X		X

PROCEDURES / ASSESSMENTS	Screening/Dispensing	2-Week Follow-up Visit	1-Month Follow-up Visit	2-Month Follow-up Visit	3-Month Follow-up Visit	Exit Visit	Unscheduled Visit	Post Study Follow-Up Visit
	Day 0	Day 10-18	Day 26-34	Day 53-67	Day 83-97			
Keratometry	X					X		
Slit Lamp Examination	X	X	X	X	X		X	X
Compare high contrast distance BSCVA to screening high contrast distance BSCVA						X		X
Compare final keratometry to screening / dispensing keratometry						X		
With Lenses Worn to Visit								
High Contrast Distance lens VA		X	X	X	X		X	
Over-refraction and distance VA		X	X	X	X		X	
Lens wettability		X	X	X	X		X	
Lens discoloration		X	X	X	X		X	
Lens deposits (type, percent and degree)		X	X	X	X		X	
Lens centration		X	X	X	X		X	
Lens movement		X	X	X	X		X	
Compare high contrast distance lens VA to high contrast distance VA at Screening / Dispensing Visit		X	X	X	X		X	
With Newly Dispensed Lenses								
High Contrast Distance lens VA	X		X	X			X	
Over-refraction and distance VA	X		X	X			X	
Lens wettability	X		X	X			X	
Lens centration	X		X	X			X	
Lens movement	X		X	X			X	
Compare high contrast distance lens VA to high contrast BSCVA	X							
Compare high contrast distance lens VA to high contrast VA at Screening/Dispensing Visit			X	X			X	

[figure not shown]
PROCEDURES / ASSESSMENTS	Screening/Dispensing	2-Week Follow-up Visit	1-Month Follow-up Visit	2-Month Follow-up Visit	3-Month Follow-up Visit	Exit Visit	Unscheduled Visit	Post Study Follow-Up Visit
	Day 0	Day 10-18	Day 26-34	Day 53-67	Day 83-97			
Study Materials								
Dispense Lenses (record lens brand, sphere power, base curve); If replacement lens, record reason for replacement	X		X	X			X	
Dispense Study kit bottles 1, 2, 3 and 4 (keep bottle 5 as a reserve at the site);	X							
Dispense Study Kit reserve (Bottle 5, if needed)		X	X	X			X	
Dispense other supplies as needed (see Protocol Section 4.4.3)	X	X	X	X			X	
Collect worn lenses from subject			X	X	X	X	X	
Collect used and unused bottles of study solutions					X	X		
Return study materials to sponsor					X	X		

[figure not shown]
^a At the screening visit, only complete the Exit Form if the subject was randomized.

[figure not shown]
^b Use provided rating scales (separate document).

[figure not shown]
Note: All VA measurements MUST be made using a phoropter.

[figure not shown]
Note: If this is an Exit Visit, also perform the procedures listed under the Exit Visit column.

[figure not shown]

[figure not shown]

[figure not shown]

[figure not shown]

APPENDIX C: SUBJECT INSTRUCTIONS

SUBJECT INSTRUCTIONS (Page 1 of 3)

PLEASE READ THESE INSTRUCTIONS CAREFULLY AND KEEP FOR FUTURE USE. DO NOT BRING WITH YOU TO THE FOLLOW-UP VISITS.

You will be participating in a study evaluating the clinical performance of two multipurpose soft contact lens care solutions. Please keep all appointments and **follow these instructions thoroughly**. If you have any questions or problems, call your study doctor. Remember to bring your glasses to all examinations.

NOTE: Wear your study lenses to each of your follow-up visits.

STUDY PRODUCT INFORMATION:

For this study, you will be using the following products:

- **Study Contact Lenses.**
 - You will be provided with new pairs of your current contact lenses at the start of the study, and then again at the 1-Month and 2-Month Follow-Up Visits.
- **A Study Kit.** You will be provided with a Study Kit that will contain:
 - **4 bottles of Study Solution each inside a white carton.** Each bottle and each carton will have an investigational label including the Study Kit number (a unique 5-digit number) and a bottle number (bottles 1, 2, 3 or 4). A fifth bottle will be retained at the site in case replenishment is required.
 - **Study Lens case.** A study lens case will be included with *each carton* of study solution for the subject to use for the month. You are required to use the study lens case.
 - **Subject Instructions.** Will be included with each carton of study solution.
- **Other Study Supplies.** The following supplies will be provided to you as needed:
 - **Carton/Bottle Return Materials.** Comprised of opaque drawstring bags and pre-printed labels for return of Study Solutions (full, partially filled, and empty bottles) to the Sponsor.
 - **Lens Return Materials.** Comprised of sealable plastic bags and pre-printed labels for return of worn lenses (in a fresh lens case with the approved saline solution) to the Sponsor.
 - **Sensitive Eyes® Rewetting Drops**

IMPORTANT SUBJECT INSTRUCTIONS:

This is a “masked” clinical study in which the Investigators and Coordinators cannot see the Study Solutions or Study Lens Cases that are dispensed to you. There will be a special study employee – the “unmasked designee” – at the site who will dispense all study materials to you in a white opaque bag and who will handle any questions you have related to the study materials.

It is very important that you do not bring the study solutions or lens cases to the study site unless they are in the white opaque bag.

SUBJECT INSTRUCTIONS (continued)

SUBJECT INSTRUCTIONS (Page 2 of 3)

GENERAL INFORMATION:

- Do NOT use any products other than those listed above or dispensed to you by your study doctor for use in this study.
- Do NOT use any other care products other than those listed above.
- Do not use any topical ocular medications (eye drops) during this study.
- Do NOT discuss or show the dispensed study products or these Subject Instructions to the Investigator or site staff during the study.
- Please save all study materials during the course of the study, and plan to bring all opened and unopened study solutions with you to the 3-month follow-up visit. Place the solution bottles back into the cartons. Place the cartons containing the bottles into the opaque drawstring bag provided. Seal the bag before going to the office.
- Always wash and rinse your hands before you handle your lenses.
- Always handle the same lens (right or left) first, to avoid mix-ups.
- Always keep the products tightly closed when not in use.
- Since you are wearing your lenses on a daily wear basis, you will be using the **Study Solution** daily to clean, rinse, disinfect and store your lenses.

PRECAUTIONS:

- Lens care procedures recommended by your study doctor must be followed.
- Failure to follow these procedures may result in the development of serious eye infections.
- Discard the **Study Solution** from the lens case after each use.
- Store **Study Solution** at room temperature
- Use **Study Solution** before the expiration date marked on the bottle label and carton.
- Do not use any eye medication in conjunction with this **Study Solution** unless under medical supervision.
- Do not touch the bottle tip of the **Study Solution** to any surface or to your eye since this may contaminate the **Study solution**.
- Keep the **Study Solution** cap closed when not in use to avoid contamination or evaporation.
- Do not use **Study Solution** with a heat disinfection method.
- Keep **Study Solution** out of reach of children.
- Consult with your study doctor if you have any allergies that may affect your ability to use the **Study solution**.

IMPORTANT:

- If irritation or excessive tearing occurs, persists or increases, or if vision is impaired, discontinue use and promptly consult your study doctor.

SUBJECT INSTRUCTIONS (continued)

SUBJECT INSTRUCTIONS (Page 3 of 3)

When used as directed, the **Study Solution**: (1) Cleans, loosens and removes accumulations of film, protein and other deposits from soft contact lenses, and (2) Rinses and stores your soft contact lenses.

GENERAL INSTRUCTIONS:

- Always wash and rinse your hands before you handle your contact lenses.
- Lenses must be thoroughly cleaned, rinsed, and soaked each time they are removed to achieve disinfection.
- Rinse each case well with the **Study Solution** before and after each use.

LENS CLEANING INSTRUCTIONS (RUB REGIMEN):

FOR DAILY CLEANING/PROTEIN REMOVAL DISINFECTION AND STORING

- Remove the right lens from your right eye.
- Place lens in lens case first
- Thoroughly rinse each side of the lens for 5 seconds with multi-purpose solution
- Place cleaned contact lenses in the lens case and fill with fresh multi-purpose solution. Soak at least 4 hours. Remember to always use fresh solution - discard solution from lens case after each use. Be sure that the lens is completely immersed in fresh **Study Solution**.
- Secure the cap and repeat the procedure with the other lens.

*Your lenses are now ready for wear. No rinse is necessary. If any debris remains on your lenses, rinse with **Study Solution** prior to insertion.*

CARE OF THE STUDY LENS STORAGE CASE:

- When the study lens case is not in use for storage of lenses, pour the **Study Solution** out of the lens case and rinse the case with fresh **Study Solution**.
- Leave the case with the caps off to dry in the air.
- For visits to the clinic, you do not need to bring the lens case to the clinic.
- If there is a reason to bring the lens case to the clinic, PLACE THE LENS CASE IN THE WHITE OPAQUE BAG FOR TRANSFER TO THE CLINIC.

REWETTING:

- If necessary, you can use the supplied rewetting drops while wearing your lenses. Simply place one or two drops of the supplied Sensitive Eyes rewetting drops in each eye and blink 2 or 3 times.
- If your lenses become dry while you are wearing them, directly apply the Sensitive Eyes rewetting drops to restore moisture and maintain comfortable lens wear.
- If lens discomfort persists, discontinue use, remove your lenses and contact your study Investigator immediately.

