4.3 Instructions for Use and Administration

Based on the randomization assignment, each randomized subject will be assigned a unique subject ID number. Each subject will be issued a Study Kit labeled with a unique Study Kit number. Subjects will be dispensed three pairs (two for back-up) of their habitual lenses at the Screening/Dispensing Visit with additional pairs of lenses being dispensed at each of the monthly follow-up visits. Subjects will wear their assigned lenses on a daily wear basis for the duration of the study.

The Investigator or designee will instruct all subjects to adhere to the Subject Instructions provided with their study lens care solution carton for daily care of their contact lenses.

In order to ensure that the Investigator and site staff remain masked to the lens care system, an unmasked designee at the site will be responsible for all dispensation and collection of study supplies to/from the subjects.

Subjects are to be instructed not to discuss or show the dispensed study products or lens care system to the Investigator or masked site staff during the study.

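### Appendix C heads the daily lens care steps as a rub regimen, but none of its five steps is a rub, so it is unclear whether subjects are to rub their lenses

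*Combined protocol and SAP*

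**What the plan says.** Section 4.3 has the Investigator or designee instruct all subjects to "adhere to the Subject Instructions provided with their study lens care solution carton for daily care of their contact lenses". Section 4.3.2 identifies those instructions as Appendix C and makes compliance mandatory. Section 4.4.2 puts a copy in each carton of solution. Section 3.1 mentions a care regimen but gives no steps.

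The regimen is on page 3 of Appendix C, under a heading that reads "LENS CLEANING INSTRUCTIONS (RUB REGIMEN". The general instructions just above it say: "Lenses must be thoroughly cleaned, rinsed, and soaked each time they are removed to achieve disinfection". Page 2 of the sheet likewise names cleaning and rinsing as separate uses of the solution: "daily to clean, rinse, disinfect and store your lenses".

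The steps listed under the heading are:

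1. Take the right lens out of the eye.
2. "Place lens in lens case first"
3. "Thoroughly rinse each side of the lens for 5 seconds with multi-purpose solution"
4. "Place cleaned contact lenses in the lens case and fill with fresh multi-purpose solution", followed by a soak of at least 4 hours.
5. Cap the case and repeat for the other lens.

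**The concern.** The heading promises an action that the steps do not contain. A subject who rubs can point to the heading, and a subject who only rinses can point to the steps. Nothing on the sheet says which of them is following it.

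This matters for two reasons that the documents themselves supply. The general instruction links cleaning, rinsing and soaking to disinfection. And Sections 5.2 and 8.6.1.4 make lens deposits a primary effectiveness endpoint, while Appendix C presents these steps as the daily cleaning and protein removal procedure. The sheet thus governs how the study solution is used on the lenses that are later graded for deposits.

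The lens wear items listed for the 3-Month visit in Section 6.1.4 count days of solution use and lens wear. None of them records technique, so those items would not show afterwards how subjects had read the sheet.

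**Working it through.** No formula applies and the plan gives no figure to reproduce. The check sets the parts of Appendix C side by side and then looks for any other text that settles the point.

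**Heading and general instruction against the steps**

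| Element | What the heading or general instruction calls for | What the five steps contain |
|---|---|---|
| Rub | Named in the heading | 0 steps |
| Clean | Listed as distinct from rinsing | No separate step; step 4 treats the lenses as already cleaned |
| Rinse | Required | 1 step, 5 seconds per side (2 × 5 = 10 seconds per lens) |
| Soak | Required | 1 step, at least 4 hours |

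Between removal from the eye (step 1) and the point where the lenses are called cleaned (step 4), the sheet asks for two things: placing the lens in the case and rinsing it. The rinse is the only one of these that could be a cleaning action. The soak comes in step 4 and is applied to lenses already given that description. A further rinse before insertion is conditional on debris remaining.

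**Step order (a lesser drafting point).** The lens is placed in the case at step 2, before the rinse, and again at step 4, after it. That is 2 placements and 0 steps taking it out.

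**Other text that might settle it**

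- Sections 4.3, 4.3.2 and 4.4.2 refer to or distribute the instructions. They contain no steps.
- Apart from this heading, the word rub occurs only in the Control's trade name (Sections 1.0, 2.0 and 4.2). A product name is not an instruction, and all subjects receive the same sheet.
- Appendix C, page 2, refers to procedures recommended by the study doctor. None is written down.

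Nothing in the text provided says whether subjects are to rub.

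**The case against.** **The steps describe one procedure and only a label is wrong.** This is fair as a description: the sheet does not print two rival regimens. But the label is the title of the procedure, and the general instruction also lists cleaning apart from rinsing. The documents do not show whether the heading or the list carries the intended meaning.

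**The solution itself cleans.** The same page credits the solution with loosening and removing deposits when used as directed, and the whole list, soak included, is headed as daily cleaning. This weakens any claim that the sheet provides for no cleaning beyond a rinse, and that claim is not made here. It does not say whether a rub is part of using the solution as directed.

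**Subjects are taught in person.** Section 4.3.2 has the unmasked designee review the instructions and the precautions for cleaning and disinfecting. Section 6.5 requires a similar review by the Investigator or designee. Section 4.6 and Appendix C, page 1, let subjects put questions to the unmasked designee. These provisions reduce the problem. They supply no written steps, so across approximately 18 sites the answer could differ.

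**Text may have been lost.** Steps 2 and 3 lack the full stops that the other steps carry, and Appendix B is not in the text provided. Lost wording cannot be excluded, but no gap is marked in Appendix C. The finding is limited to the text provided.

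**Stronger readings that the documents do not support.** A reader might cite the page 2 warning, "Failure to follow these procedures may result in the development of serious eye infections", as a statement about this step list. The sentence before it concerns procedures recommended by the study doctor, and the warning refers to those. A reader might also infer a bias between arms or a loss of power on the deposits endpoint. Both arms receive the same sheet, and nothing in the documents links its wording to a change in the proportion of eyes with no or light deposits.

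**Conclusion.** The point holds as an internal contradiction in the instructions that every subject must follow. The heading and the general instruction do not match the steps, and whether subjects are to rub is unclear. The textual gap is 5 steps, 0 rubs, and a single rinse of 5 seconds per side before the lenses are called cleaned. The double placement in the case is secondary.

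The consequence for deposits or safety cannot be given a size or a direction from the documents. The conclusion assumes that Appendix C as supplied is complete and that no written regimen exists in material not provided. The correction should be made because the sheet governs use of the study product and is cheap to put right, not because any bias has been shown.

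**What to change.** Reconcile the heading, the general instructions and the step list in Appendix C so that they describe one regimen in one clear order, including where the lens is when it is rinsed. Obtain IRB review of the revised subject material and issue the new insert, preferably before cartons are packed. The unmasked designee's review under Section 4.3.2 and the review under Section 6.5 should then use the same text. Which regimen is right is for the sponsor to settle; this review takes no view.

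The cost is the redrafted page, one IRB review and a reprint. Section 4.4.2 provides one instruction sheet per carton and five cartons per kit, so 252 subjects need about 252 × 5 = 1,260 inserts, before any replacement kits. Sample size, visit schedule and analysis are unaffected.
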